After consent has been obtained, a member of the research team will record participant demographics, medical/surgical history and perform measurement of anthropometrics (height, weight, waist circumference, blood pressure and pulse rate) for all the patients in line with study Standard Operating Procedures (SOPs) and arrange for standard laboratory testing (HbA1c, FBC, U+Es, lipids, LFTs, TFTs) and pregnancy test (for females of childbearing potential). A urine ACR will be performed for patients with prediabetes, diabetes and hypertension. The King's College Obesity Staging assessment will be recorded in the CRF if it is available in the patient's notes. A Stop Bang questionnaire will be undertaken (to capture any undetected OSA cases) and an Epworth Sleepiness Scale (to capture daytime sleepiness) will be undertaken by all participants. Participants with undetected OSA defined as a score between 5-8 on the Stop Bang, will be informed that they are at high risk of this sleep disorder and a referral to the sleep clinic from the local PI will be made so that the participant can be considered for investigation. All sleep related therapy will then be the responsibility of the local sleep clinic as per standard practice.

Those participants that are already patients of the sleep clinic will have their notes reviewed to determine whether or not they are CPAP compliant and thus 'successful' against the below criteria.

- a. CPAP usage \geq 4 hrs/night = successful
- b. CPAP usage < 4 hrs/night = struggling
- c. CPAP usage \leq 1 hrs/night = failure

A repeat screening visit may take place if indicated for eligibility (for example, repeat blood pressure measurement for patients with undiagnosed hypertension). The study clinician will assess and decide when all the blood results and investigations are available whether a patient is eligible for randomisation or not.

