8.3.2 Weeks 52 and 104 – All Participants

The Data Collection Visits at Weeks 52 (\pm 3 months*) and 104 (\pm 14 days) will take place at the study site for all participants in both study groups. Weight, waist circumference, blood pressure and pulse rate will be recorded in line with study SOPs, any AEs/SAEs will be noted, and documentation of inclusion/exclusion criteria and changes in medication and/or diseases will be performed. Blood samples for standard laboratory testing of biochemical outcomes (HbA1c, FBC, U+Es, lipids, LFTs, TFTs, amylase) will be taken and participants will be requested to complete research questionnaires (see Appendix 3). A pregnancy test will take place for all female participants of child-bearing potential (in both standard care and LIRA 3mg targeted prescribing pathway groups).

A urine ACR will be performed for participants with diabetes, prediabetes and hypertension. All participants will complete the Epworth Sleepiness Scale to capture any improvement/decline in daytime sleepiness during the course of the study and the Stop Bang questionnaire to capture any undetected OSA cases, at 3 data collection visits (Baseline, Weeks 52 and 104). OSA patients will be managed through their local sleep clinic as per standard care. Those participants that are patients of the sleep clinic will have their notes reviewed to determine whether or not they are CPAP compliant and thus ‘successful’ against the below criteria.

- a. CPAP usage \geq 4 hrs/night = successful
- b. CPAP usage $<$ 4 hrs/night = struggling
- c. CPAP usage \leq 1 hrs/night = failure

Additional procedures at **Weeks 52 and 104** for the participants in the standard care group who have been prescribed and started anti-obesity medications (for example Orlistat) will be to ascertain whether they are still on the medication, their adherence, and any side effects.

Additional procedures at the **Week 52** visit for all participants who are on **LIRA 3mg** will include:

- Identification of participants on LIRA 3mg who have lost $\geq 15\%$ weight loss and meet the pre-specified criteria to continue on LIRA 3mg. These participants will meet the study clinician in order to be offered LIRA 3mg for another 52 weeks, to receive a new prescription of LIRA 3mg and to discuss adherence with the treatment and any side effects. Pregnancy testing will be undertaken as standard for this visit and clear instructions regarding contraception until the end of the study will be provided

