For patients on LIRA 3mg, monitoring of any problems and side effects, adherence with the injection, and advice on dose titration (at Weeks 2 and 4) as per the pre-specified protocol will take place during these visits. A pregnancy test will take place for all female participants of child-bearing potential who are in the targeted prescribing pathway and continue to be eligible to receive supply of LIRA 3mg. Clear instructions regarding contraception until the end of the study will be given at each visit.

Additional procedures at the **Week 16** visit for all participants who are on **LIRA 3mg** will include:

- Identification of participants on LIRA 3mg who have lost $\geq 5\%$ weight loss and meet the pre-specified criteria to continue on LIRA 3mg. These participants will meet the study clinician in order to be offered LIRA 3mg for another 16 weeks, to receive a new prescription of LIRA 3mg and to discuss adherence with the treatment and any side effects. Pregnancy testing will be undertaken as standard for this visit and clear instructions regarding contraception until the end of the study will be provided.
- Participants on LIRA 3mg who did not reach the target of $\geq 5\%$ weight loss will meet the study clinician who will explain to them that they cannot continue on the medication any longer and that they will instead continue in the study on the Tier 3 programme with standard care. These participants will remain in the intervention group (targeted prescribing pathway), but will not receive LIRA 3mg as per the pre-specified stopping rules.

Additional procedures at the **Week 32** visit for all participants will include:

- Blood samples for standard laboratory testing of biochemical outcomes (HbA1c, FBC, U+Es, lipids, LFTs, TFTs, amylase) will be taken for all participants
- A urine ACR will be performed for participants with diabetes, prediabetes and hypertension for all participants
- Participants in the standard care group who have been prescribed and started on anti-obesity medications (for example Orlistat) will be monitored to ascertain whether they are still on the medication, their adherence, and any side effects

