As a result of conducting virtual consultations and telephone calls, the following procedures will not be performed during the COVID19 pandemic, therefore have been halted as an urgent safety measure:

- BP and Pulse measurements – Participants who are known to have hypertension have home BP monitoring machines and their BP measurements are being collected and assessed by the study team during remote visits. There is no undue risk for those who do not have hypertension, as Liraglutide is not related to BP, and participants are all established on the drug.
- Bloods (lipids, renal, LFTs, thyroid, FBC & HbA1c, amylase) at V9, 11 & 13/15 only - The amylase test usually taken at visits 9, 11 & 15 is a safety blood in relation to pancreatitis. During the remote visits, all participants will be monitored for any new symptoms which will be appropriately managed by the study clinical team. The small number of participants who have diabetes will regularly check their blood glucose at home as usual. All other bloods are taken to assess efficacy, therefore not conducting them will have no impact on participant safety. All participants will be asked to report AE/SAE during remote visits.
- ACR urine test – Not conducting this poses no additional risk to participants.

Once restrictions due to the COVID19 pandemic have been lifted, a further risk assessment will be completed and in agreement with the Sponsor, Study team and NHS Host Organisations, face to face visits will be re-implemented. For the avoidance of doubt, virtual consultations will still be an option for study visits, as preferred by the participant or recommended by the study clinician, to aid the retention of participants and study visit attendance and collection of primary outcome data (via self-reported weight measurement data).

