10.1.1 Adverse Event (AE)

An AE or adverse experience is:

Any untoward medical occurrence in a patient or clinical investigation participants administered a medicinal product, which does not necessarily have to have a causal relationship with this treatment (the study medication).

An AE can therefore be any unfavourable and unintended sign (including an abnormal laboratory finding), symptom or disease temporally associated with the use of the study medication, whether or not considered related to the study medication.

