Adherence with other anti-obesity medications [#]								X		X	X				X
Adherence to Tier 3 (or equivalent) Service			X	X	X	X	X	X	X	X	X	X	X	X	X
Contacts with GP/HCP		X	X	X	X	X	X	X	X	X	X	X	X	X	X
Inpatient and Outpatient apt's		X	X	X	X	X	X	X	X	X	X	X	X	X	X
Medications cost		X									X				X
QUESTIONNAIRES^{^^^}															
HSRUQ		X									X				X
TSQM###		X									X				X
EQ-5D		X									X				X
IWQOL-Lite		X									X				X
IPAQ-Long		X									X				X
PHQ-9		X									X				X

*Only for participants at the LIRA 3mg group who are on active treatment

^{§§}Target dose by week 8. ^{§§}Optional Telephone calls to check tolerance and up-titrate at weeks 1, 3 & 5.

**As required for participants with identified risk OSA or current OSA based on CPAP use and type of CPAP (variable or fixed pressures CPAP)

*** Only for prediabetic, diabetic and hypertensive individuals

****Where possible the week 52 visit should continue to be scheduled within the (± 14 days) study visit window, however to aid retention

and to help maximise data collection for the study primary end point, the week 52 visit window can be extended to ± 3 months.

Only for participants in the standard care group on treatment with anti-obesity drugs

#[#] Only for participants with diagnosis of T2DM

#^{##} For participants on treatment either with LIRA 3mg or other anti-obesity medication

[^] Only participants who report problems with injection and/or side-effects may be reviewed by study clinician

^{^^} A repeat screening visit may take place to assess eligibility

Drug dispensing unscheduled visits may occur at any point within the study period for participants in LIRA3 mg group as required (not depicted above)

^{^^^}In response to the COVID19 global pandemic, an interim time point for the quality of life questionnaires has been added (HSRUQ, TSQM, EQ-5D, IWQOL-Lite, IPAQ-Long and PHQ-9). These will be sent out to all participants during the COVID19 pandemic.

^{^^^^} These activities will not be completed during the COVID19 pandemic restriction period, however once restrictions are lifted participants that resume face to face visits will be completed as per the original protocol.

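### The protocol text schedules follow-up amylase for everyone but Appendix 3 only for participants on LIRA; if the appendix was followed, the SAP's AE comparisons could reflect unequal testing

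*Protocol*

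**What the plan says.** **Follow-up, Protocol text.** For week 32, Section 8.4 states: "Blood samples for standard laboratory testing of biochemical outcomes (HbA1c, FBC, U+Es, lipids, LFTs, TFTs, amylase) will be taken for all participants". Section 8.3.2 says the week 52 and 104 visits "will take place at the study site for all participants in both study groups", and its blood list includes amylase with no restriction by arm.

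**Follow-up, Appendix 3.** Every amylase cell after screening is X*. The footnote to the asterisk reads: "Only for participants at the LIRA 3mg group who are on active treatment".

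**COVID section (8.10).** The halted procedures include "Bloods (lipids, renal, LFTs, thyroid, FBC & HbA1c, amylase) at V9, 11 & 13/15 only". The same bullet then says: "The amylase test usually taken at visits 9, 11 & 15 is a safety blood in relation to pancreatitis".

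**Screening.** Section 8.2 lists "standard laboratory testing (HbA1c, FBC, U+Es, lipids, LFTs, TFTs) and pregnancy test", without amylase. Appendix 3 has an unrestricted amylase cell at screening, and Section 7.3 excludes patients whose amylase is more than three times the upper normal limit.

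**Route to the results.** Under Section 10.1.1 an AE can be any unfavourable and unintended "sign (including an abnormal laboratory finding), symptom or disease temporally associated with the use of the study medication". SAP section 6 reports AE incidence by treatment for each System Organ Class (SOC) and each expected AE type. It also summarises safety by whether the participant was currently receiving LIRA. The templates in SAP 16.15 add an incidence rate ratio. The SAP does not say who was tested for amylase.

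**The concern.** A comparison of laboratory-detected events is fair only if both groups are looked at equally often. Under the text, each participant has three scheduled follow-up tests whatever the arm. Under the appendix, controls have none, and intervention participants have one only while still on the drug. An asymptomatic rise could then be found on schedule in one group and not in the other, even with the same underlying rate.

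The by-arm tables would be affected, and the split by current LIRA receipt more so, because under the appendix scheduled testing coincides with being on treatment. Section 8.10 describes amylase as a safety test for pancreatitis, which Section 14.10.1 names among the rare serious risks. At low event counts, a few test-driven AEs can move a rate ratio. If sites differed in which passage they followed, detection would also vary by site.

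**Working it through.** The plan gives no figure for this point. The check sets the passages side by side and counts scheduled tests.

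**Step 1: who is tested after screening.**

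| Source | Week 32 | Week 52 | Week 104 |
|---|---|---|---|
| Sections 8.4 and 8.3.2 | both arms | both arms | both arms |
| Appendix 3 (X*) | on LIRA only | on LIRA only | on LIRA only |
| Section 8.10, whole panel | visit 9 | visit 11 | visit 13 or 15 |
| Section 8.10, amylase sentence | visit 9 | visit 11 | visit 15 |

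**Step 2: is the asterisk deliberate?** The amylase cells are out of line in the text version of Appendix 3; read literally they fall under weeks 40, 65 and 104. The visits are therefore inferred from Section 8.10 and from the ACR row, whose cells fall on weeks 32, 52 and 104. The asterisk itself looks intended. The cells of the other blood rows carry none. The pregnancy-test row uses X* at interim visits but plain X at weeks 52 and 104, which agrees with Section 8.3.2, where both groups are tested. The table therefore uses the mark to separate who is tested.

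**Step 3: what Section 8.10 adds.** In Appendix 3 the week 104 visit is number 15 for participants on active LIRA and 13 otherwise. The panel, which names amylase, is given at 13/15, so it covers both. The amylase sentence gives 15 alone, which leans towards the appendix. Visits 9 and 11 carry the same number in both arms and settle nothing. The pandemic halt does not explain the conflict, because the sentence describes usual practice.

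**Step 4: scheduled follow-up tests.** Inputs: 131 control and 261 intervention participants (Protocol 11.2) and three visits.

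- Text: control 131 x 3 = 393; intervention 261 x 3 = 783. That is three per person in each arm.
- Appendix 3: control 131 x 0 = 0; intervention at most 783, and fewer in practice because testing ends when LIRA stops.
- Difference in control tests: 393 - 0 = 393. Applying the plan's 25% dropout allowance to all three visits, as an illustration, gives 393 x 0.75 = about 295.

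The COVID halt lowers these counts further. The documents do not say how many visits it affected, so that reduction cannot be calculated.

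**The case against.** Several points on the other side stand.

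- **AEs in controls remain possible.** A reader might infer that amylase AEs could occur only in the LIRA arm. That does not follow. Appendix 3 governs scheduled tests. Section 8.8.3 contemplates testing when pancreatitis is suspected, and routine care may include amylase. What the appendix removes is scheduled detection of asymptomatic rises in controls.
- **A raised value is not automatically an AE.** Section 10.1.1 says an abnormal laboratory finding can be one, and Section 10.7 refers to clinically significant values. Investigators retain judgement.
- **No event count can be supported.** A reader might convert the gap in testing into a number of excess AEs. That needs the fractions still on LIRA at each visit, the proportion of results flagged and the extent of the COVID halt. The documents give none of these.
- **The evidence is not all one way.** Section 8.10 is mixed. Table 1 lists amylase among the bloods, but its column alignment is broken and it does not settle the matter.
- **The SAP offers some protection.** Section 6 lists every AE with relatedness, severity and action taken, and safety outcomes are not formally tested. The listings would let a reader find amylase AEs, but they do not show who was tested.
- **Timing.** The SAP draft is dated 01/08/2022, after the 30/06/2022 study end date in the protocol's amendment history. Correcting the protocol cannot change who was tested. Reporting can still be changed, because the SAP is marked as a draft and is to be finalised before database lock.

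The objection also bears on the remedy. Taking amylase-only AEs out of the main rate ratios could hide a real signal in the drug arm, so they should not be removed.

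**Conclusion.** The contradiction is real at all three follow-up visits, and the screening list in Section 8.2 has a related gap. The size that can be stated is the number of scheduled control tests: up to 393 under the text and 0 under Appendix 3, at the planned sample size and before dropout and the COVID halt.

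The effect on the results is conditional. If Appendix 3 was followed, scheduled detection of asymptomatic amylase rises is confined to participants on LIRA. The SOC and expected-AE rates and ratios, and the summaries by current LIRA receipt, could then partly reflect unequal testing. If the text was followed, the schedule creates no such imbalance between arms. The documents do not show which passage sites used. Amylase is not an efficacy endpoint, so the primary outcome is not touched. The conclusion assumes that the X* cells belong to weeks 32, 52 and 104, as Section 8.10 and the text indicate.

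**What to change.** 1. Reconcile Protocol Sections 8.2, 8.3.2, 8.4 and 8.10 with Appendix 3 on who has amylase taken and when. Record which schedule each site actually used.
2. In SAP section 6, tabulate the amylase tests done by arm and site at weeks 32, 52 and 104.
3. Flag AEs whose only basis is a scheduled amylase result. Keep them in the main AE tables, with a footnote stating who was tested.
4. Show the affected SOC and expected-AE rate ratios a second time without the flagged AEs, as a sensitivity display.

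The cost is a document correction, one extra table and one sensitivity line. No data are dropped from the main safety tables.

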After 32 weeks (\pm 14 days) on the medication, only those participants who have lost $\geq 10\%$ of their baseline weight and are still on treatment with LIRA 3mg will be offered another 20 weeks on LIRA 3mg. Participants who have not met this weight loss target will have their LIRA 3mg treatment stopped but will still continue in the targeted prescribing pathway but will receive standard care only during the remainder of the study.

3rd stopping rule: After the first year of treatment (week 52; \pm 14 days), only those participants who have lost $\geq 15\%$ of their baseline weight and are still on treatment with LIRA 3mg will be offered another 52 weeks on LIRA 3mg. Participants who have not met this weight loss target will have their

LIRA 3mg treatment stopped and will still continue in the targeted prescribing pathway but will receive standard care only during the remainder of the study.

Participants who fail to reach the pre-defined weight-loss targets to continue LIRA 3mg treatment, or who choose to stop receiving LIRA 3mg, will continue to be offered the standard care provided by the Tier 3 service. These participants will still attend the Clinical Review Visits but not the additional visits for participants who are still on LIRA 3mg (e.g. Weeks 65 & 91) because these visits will not be relevant to them; visits at Weeks 65 and 91 are intended to provide a new prescription of LIRA 3mg and to discuss adherence and any side effects; see Appendices 2 & 3).

Participants will remain routinely in the Tier 3 service in-line with NICE guidance throughout the duration of the research study. Participants may be offered treatment options within the duration of the study, including bariatric surgery, as per NICE guidance and according to the decision of the local Tier 3 Multidisciplinary Team. Participants who have undergone bariatric surgery after randomisation will only be included in the intention to treat (ITT) analysis. This decision was made because the proportion of participants undergoing bariatric surgery is likely to be unbalanced between the treatment groups (i.e. more participants in the control group are expected to have bariatric surgery than in the targeted prescribing pathway treatment group), and thus weight loss in these individuals could unduly influence the study results. Participants who have been prescribed and start anti-obesity medication (such as Orlistat) will be ineligible for LIRA 3mg treatment.

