*Where possible the week 52 visit should continue to be scheduled within the (± 14 days) study visit window, however to aid retention and to help maximise data collection for the study primary end point, the week 52 visit window can be extended to ± 3 months.

8.4 Clinical Review (safety and retention) Visits (Weeks 2, 4, 8, 12, 16, 20, 32, 40 and 78) – All Participants

The Clinical Review visits will take place with a member of the research team at the study site. Where appropriate, the Clinical Review visits will be arranged in conjunction with the standard Tier 3 service appointments that participants will be scheduled to attend (e.g. appointments with the dietitian). Additional study visits will be arranged in the event where this might not be possible. The participant appointment schedule will depend on the Tier 3 service schedule, the date of the required Clinical Review Visit, and the availability of participants. The participant's adherence to the Tier 3 programme will also be reviewed. The research team will endeavour to maintain a low level of burden for these multiple visits. For participants in both arms of the study visits held at 2/52 (visit 3), 4/52 (visit 4), 12/52 (visit 6), 20/52 (visit 8), 40/52 (visit 10) and 78/52 (visit 12 for LIRA arm/13 for control arm) will be defined as 'optional' to reduce study burden and maximise participant retention, as per the visit schedule. Our experience in undertaking successful longitudinal research with multiple follow-ups will support these follow-up visits. The frequency of appointments for the Tier 3 service offered to the participants in both groups will continue as per the standard practice for each Tier 3 service.

During these Clinical Review Visits, participant eligibility will be re-checked and consent for continuation in the study will be re-confirmed. Weight, waist circumference, blood pressure and pulse rate will be recorded in line with study SOPs, any AEs/SAEs will be noted, and documentation of inclusion/exclusion criteria and changes in medication and/or diseases will be performed.

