- Participants on LIRA 3mg who have lost $\geq 10\%$ weight loss and meet the pre-specified criteria to continue on LIRA 3mg. These participants will meet the study clinician in order to be offered LIRA 3mg for another 24 weeks, to receive a new prescription of LIRA 3mg and to discuss adherence with the treatment and any side effects. Pregnancy testing will be undertaken as standard for this visit and clear instructions regarding contraception until the end of the study will be provided
- Participants on LIRA 3mg who did not reach the target of $\geq 10\%$ weight loss will meet the study clinician who will explain to them that they cannot continue on the medication any longer and that they will instead continue in the study on the Tier 3 programme with standard care. These participants will remain in the intervention group (targeted prescribing pathway) for the purpose of analysis, but will not receive LIRA 3mg as per the pre-specified stopping rules.

8.4.1 Additional Clinical Review (safety and retention) Visits for LIRA 3mg group (Weeks 65 and 91)

These two additional Clinical Review visits will take place with a member of the research team at the study site for only those participants in the intervention group who are still on treatment with LIRA 3mg. The agenda for these visits will be identical to the other nine Clinical Review Visits as described above in Section 8.4. The purpose of these visits is to provide participants with a new prescription of LIRA 3mg and to discuss adherence with the treatment and any side effects.

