After 32 weeks (\pm 14 days) on the medication, only those participants who have lost $\geq 10\%$ of their baseline weight and are still on treatment with LIRA 3mg will be offered another 20 weeks on LIRA 3mg. Participants who have not met this weight loss target will have their LIRA 3mg treatment stopped but will still continue in the targeted prescribing pathway but will receive standard care only during the remainder of the study.

3rd stopping rule

After the first year of treatment (week 52; \pm 14 days), only those participants who have lost $\geq 15\%$ of their baseline weight and are still on treatment with LIRA 3mg will be offered another 52 weeks on LIRA 3mg. Participants who have not met this weight loss target will

have their LIRA 3mg treatment stopped and will still continue in the targeted prescribing pathway but will receive standard care only during the remainder of the study.

Participants who fail to reach the pre-defined weight-loss targets to continue LIRA 3mg treatment, or who choose to stop receiving LIRA 3mg, will continue to be offered the standard care provided by the Tier 3 service. These participants will still attend the Clinical Review Visits but not the additional visits for participants who are still on LIRA 3mg (e.g. Weeks 65 & 91) because these visits will not be relevant to them; visits at Weeks 65 and 91 are intended to provide a new prescription of LIRA 3mg and to discuss adherence and any side effects).

Participants will remain routinely in the Tier 3 service in-line with NICE guidance throughout the duration of the research study. Participants may be offered treatment options within the duration of the study, including bariatric surgery, as per NICE guidance and according to the decision of the local Tier 3 Multidisciplinary Team.

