1.3 Visit schedule

The original visit schedule was as follows:

- Screening and Consent Visit (Day -42 to -1)
- Data Collection Visits – All participants
 - Baseline Visit (Day 0) - including randomization and treatment initiation for participants randomized to the intervention arm
 - Week 52
 - Week 104

- Clinical Review (safety and retention) Visits – All participants
 - Weeks 2, 4, 8, 12, 16, 20, 32, 40, and 78
- Additional Clinical Review (safety and retention) Visits for LIRA 3mg group
 - Weeks 65 and 91

In response to the COVID-19 global pandemic, an interim time point for the quality-of-life questionnaires was added. The following questionnaires were sent out to all participants during the COVID-19 pandemic:

- Health Services and Resources Use Questionnaire (HSRUQ)
- Treatment Satisfaction Questionnaire for Medication (TSQM)
- European Quality of Life -5 Dimensions (EQ-5D)
- Impact of Weight on Quality of Life-Lite (IWQOL-Lite)
- International Physical Activity Questionnaire-Long (IPAQ-Long)
- Patient Health Questionnaire-9 (PHQ-9).

Where possible, the week 52 visit continued to be scheduled within the \pm 14 days study visit window, however to aid retention and to help maximise data collection for the study primary end point, the week 52 visit window could be extended to \pm 3 months. Where it was not possible to conduct a week 52 visit (e.g., because of COVID-19 restrictions in place at the time), weight data were obtained from the participant's hospital, GP or health record instead where a measurement was available within a window of +/- 12 weeks from the scheduled week 52 visit to ensure that the primary outcome was as complete as possible.

2 Outcomes and other variables

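### Protocol 8.4 offers 24 weeks of liraglutide at week 32 where the stopping rules require 20, and the week-32 responder row in SAP 14.1 is mislabelled

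*Protocol*

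**What the plan says.** **Length of the week-32 offer.** Protocol 8.4, under the additional week-32 procedures, has participants on liraglutide with at least 10% loss meet the study clinician "in order to be offered LIRA 3mg for another 24 weeks". The second stopping rule in Protocol 6.2 says that participants who reach 10% and remain on drug "will be offered another 20 weeks on LIRA 3mg". SAP 1.2.3.1 gives the same rule for those who have reached the target and "are still on treatment with LIRA 3mg will be offered another 20 weeks on LIRA 3mg". The third stopping rule in Protocol 6.2 opens "After the first year of treatment (week 52" and gives a margin of ±14 days.

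**Adherence table.** SAP Appendix 7, table 14.1, sorts intervention participants by how far they got through the stopping rules and compares days on liraglutide with 70% of the days to week 16, 32 or 52. Where the visit date is missing, fixed cut-offs of 78, 156 and 254 days apply. The third row describes people who met the week-16 rule but not the week-32 rule, then gives at least 10% weight loss in brackets and uses week 52 as the denominator.

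**Timing of week 52.** The footnote to Protocol 8.3.2 says that "the week 52 visit window can be extended to" ±3 months. SAP 1.3 says that "the week 52 visit window could be extended to" the same limits, and accepts weights from routine records "within a window of +/- 12 weeks from the scheduled week 52 visit" where no visit was possible.

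**The concern.** The visit instructions in Section 8.4 are what a site works from on the day, and they give a treatment block four weeks longer than the stopping rule it implements. SAP 3.3.3 removes from the per-protocol set anyone who took liraglutide after a stopping rule should have ended it, so the planned end of each block needs to be unambiguous.

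The label in 14.1 matters because the table decides who counts as having taken 70% of planned doses at 52 weeks. Taken literally, the second and third rows both describe people who failed the week-32 rule, and nobody who passed it has a row.

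A smaller question is whether the week-52 denominator still represents planned doses when the visit falls well outside ±14 days. At stake are the per-protocol analysis (SAP 3.3.3), the exploratory analysis built on it (SAP 5.4.4) and the liraglutide adherence outcome (SAP 2.2.1).

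**Working it through.** **1. Which duration fits.** End of block = 32 + weeks offered.
- Protocol 6.2 and SAP 1.2.3.1: 32 + 20 = week 52, the third stopping rule.
- Protocol 8.4: 32 + 24 = week 56. That is 56 − 52 = 4 weeks past the rule. The rule's outer limit is 52 + 2 = week 54, so it is also 56 − 54 = 2 weeks past that.
- The other offers in the visit instructions end exactly on the next decision or on the end of study: 16 + 16 = 32 (Section 8.4) and 52 + 52 = 104 (Section 8.3.2). Only the week-32 figure is out of step.

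**2. Which duration the SAP used.** Fallback cut-off = 0.70 × 7 × weeks.
- Week 16: 0.70 × 112 = 78.4 (SAP: 78).
- Week 32: 0.70 × 224 = 156.8 (SAP: 156).
- Week 52: 0.70 × 364 = 254.8 (SAP: 254).
- Week 56, for comparison: 0.70 × 392 = 274.4, which the SAP does not use.

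The three fallbacks in 14.1 are reproduced, and the last confirms a 52-week plan.

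**3. The row label, side by side.**
- 14.1, second row: week-16 rule met, week-32 rule not met, loss below 10% or not measured, denominator to week 32.
- 14.1, third row: week-16 rule met, week-32 rule not met, loss of at least 10%, denominator to week 52.
- 14.2, third and fourth rows: week-16 rule met, week-32 rule met, loss of at least 10%.

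The bracketed threshold, the week-52 denominator and 14.2 all show that the third row of 14.1 is meant for people who met the week-32 rule.

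**4. Late week-52 visits (optional point).** Assume that three months is 13 weeks (91 days), so the latest visit is day 364 + 91 = 455.
- Cut-off: 0.70 × 364 = 254.8 days on time, and 0.70 × 455 = 318.5 days at the latest date.
- Last dose on day 300: 300/364 = 82.4% (adherent) with an on-time visit, and 300/455 = 65.9% (non-adherent) with the latest one.
- Last doses on days 255 to 318 change class between those two dates.
- Liraglutide taken to day 364 stays adherent even with the latest visit: 364/455 = 80.0%.

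**The case against.** **On the 24 weeks.** Section 8.3.1.2 refers to Section 6.2 for the stopping rules, and Section 8.3.2 independently requires liraglutide to stop at the week-52 visit when 15% is not reached. A reader might infer that Section 8.4 permits treatment past that decision; these provisions show that it does not. That limits the consequence but leaves the number wrong. Nor does a supply margin explain it: a 14-day window accounts for two weeks, not four, and the key to Appendix 3 already states "Drug dispensing unscheduled visits may occur at any point within the study period" for the liraglutide group.

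**On the label.** A reader might infer that week-32 non-responders would be judged against 52 weeks, so that someone correctly stopped on day 224 would score 224/364 = 61.5% and be excluded. The documents do not support this. The second row already covers losses below 10% with its own week-32 denominator, so the intent is clear and the error is editorial.

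**On the moving denominator.** A reader might infer that the week-52 adherence rule is itself an error. The documents do not show that, for four reasons.
- Section 8.3.2 applies the 15% rule at a week-52 visit now allowed at ±3 months. Days to that visit can therefore be the planned exposure, as in the rows for weeks 16 and 32.
- For early visits, the actual date is the better denominator. Someone stopped by the rule on day 273 who took 240 of the permitted days has 240/273 = 87.9%; forcing day 364 gives 240/364 = 65.9% and fails them wrongly.
- SAP Appendix 7 uses a recorded last-dose date only where one exists. Otherwise the numerator is also a visit date and may move with the denominator.
- Record weights are used where no week-52 visit could be held. The natural reading is that the visit date is then missing and the 254-day fallback applies, although the SAP does not say so.

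What stands is a narrow ambiguity for late visits, when the stop is dated and planned supply ended at week 52.

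**Conclusion.** Two small errors hold as written. Protocol 8.4 overstates the week-32 offer by four weeks. The third row of SAP 14.1 carries a label that contradicts its own threshold, leaving week-32 responders without a correct row. The two are independent: the SAP's cut-offs rest on 52 weeks, so the 24-week text does not feed the adherence rule.

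The late-visit point is optional and is not an error as written. It rests on three months being 13 weeks, on a dated stop between days 255 and 318, and on supply planned only to week 52. The number of such participants cannot be derived from the documents.

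The severity is minor. The primary analysis uses complete cases and the ITT analysis uses all randomised participants; neither depends on adherence status. Sample size and power are likewise untouched.

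**What to change.** 1. In Protocol 8.4, change 24 weeks to 20. If dosing is complete, record a clarification in the trial file instead. This is likely: the last amendment set the study end at 30/06/2022 and the SAP is dated 01/08/2022.
2. In the third row of SAP 14.1, correct the label to say that the week-32 rule was met, as in 14.2.
3. Optionally, add a sentence to the third row of 14.1 and the week-52 row of 14.2. For late visits only, cap both the days on liraglutide and the denominator at the planned end: day 364, or day 378 if the 14-day window is allowed (cut-off 0.70 × 378 = 264.6 days). Keep the actual date for early visits at which the stopping rule was applied. The cap should not be used where supply was deliberately extended to the late visit: a stop on day 260 would then pass at 260/364 = 71.4% although only 260/455 = 57.1% of the supplied period was taken.

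The cost is one number, one label and, if wanted, one sentence. The SAP is still marked draft and is due to be finalised before database lock. No visits, data or participants are added.
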